3.5.4 Definition of Baseline

For all analyses, Baseline will be defined as the last non-missing evaluation prior to the first dose date/time. For cohort A7, Period 2 Baseline will be defined as last non-missing evaluation prior to the dosing on Period 2 Study Day 1.

For all cohorts, except cohort A7 Period 2, Change from Baseline will be defined as the result at desired timepoint minus the result at Baseline. For cohort A7 Period 2, Change from Baseline will be defined as the result at desired timepoint minus the result at Period 2 Baseline.

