3.5.5 Analysis Visit Windows

Analysis visit windowing will not be used for this study. Nominal scheduled study visits will be used as analysis visits. Unscheduled visits and premature termination visits that occur on or in place of a scheduled study visit will be mapped to the same analysis visit as the scheduled study visit.

3.5.6 Selection of Data in the Event of Multiple Records on Same Analysis Visit Day

Depending on the statistical analysis method, single values may be required for each analysis visit day. If a single value is needed, but multiple valid, nonmissing measurements exist in an analysis visit day, records will be chosen based on the following:

- For Baseline, the last nonmissing value on or prior to the first dose date of study drug will be selected, unless specified differently. If there are multiple records with the same time or no time recorded on the same day, the record with the lowest accession number will be used.
- For post-Baseline values, the latest record will be selected. If there is more than 1 record with sample collected on the same day with the same time, the retest record will be selected. If there is no clear indication for which record is the retest record, then the record with the lowest accession number will be used.

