5.2.3 Summaries of Numeric Laboratory Results

Descriptive statistics will be provided by treatment and cohort for each laboratory test specified in the study protocol as follows:

- Baseline values
- Values at each post-Baseline visit
- Change from Baseline at each post-Baseline visit

A Baseline laboratory value will be defined as the last measurement obtained on or prior to the date/time of first dose of study drug. Change from Baseline to a post-Baseline visit will be calculated for any post-Baseline visit including follow-up visits. For Cohort A7 Period 2, Period 2 Baseline and Change from Period 2 Baseline will be used instead.

In the case of multiple values in a visit day, data will be selected for analysis as described in [Section 3.5.6](#).

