5.3 Body Weight and Vital Signs

Descriptive statistics will be provided by treatment and cohort for body weight, BMI, and vital signs (systolic and diastolic blood pressure [mmHg], pulse [beats/min], respiration [breaths/min], and body temperature [°C]) as follows:

- Baseline value
- Values at each post-Baseline visit
- Change from baseline at each post-Baseline visit

A Baseline value will be defined as the last available value collected on or prior to the date/time of first dose of study drug. Change from Baseline to a post-Baseline visit will be calculated for any post-Baseline visit including follow-up visits.

For Cohort A7 Period 2, Period 2 Baseline and Change from Period 2 Baseline will be used instead.

In the case of multiple values in an analysis window, data will be selected for analysis as described in [Section 3.5.6](#).

A by-subject listing of vital signs will be provided by cohort, subject number, and visit in chronological order. In the same manner, a by-subject listing of body weight, height, and BMI will be provided separately.

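### As written, SAP 5.3 and 3.5.6 let the 12 h vital-sign reading alone represent each dosing day, so the 2, 4 and 8 h readings are listed but never tabulated

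*Combined protocol and SAP*

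**What the plan says.** SAP 5.3 plans descriptive statistics for vital signs in three forms: Baseline, "Values at each post-Baseline visit", and change from Baseline at each such visit. It names no table by hour, no minimum or maximum, and no abnormality table. It then gives a cross-reference to Section 3.5.6: "In the case of multiple values in an analysis window, data will be selected for analysis as described in" that section.

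SAP 3.5.5 defines the unit: "Nominal scheduled study visits will be used as analysis visits". SAP 3.5.6 applies under a condition, "If a single value is needed, but multiple valid, nonmissing measurements exist in an analysis visit day", and its rule is "For post-Baseline values, the latest record will be selected".

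The collection schedule is in the protocol:

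- **Part A** (Appendices 1a and 1b, footnote a): predose on Day 1, then 2, 4, 8, 12, 24, 48, 72, 96, 120 and 144 h after the dose.
- **Part B** (Appendix 2, footnote a): predose, 2, 4, 8 and 12 h on each of Days 1 to 8, then daily through 5 days after the last dosing day, and once at end of study.

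A listing is also planned: "A by-subject listing of vital signs will be provided by cohort, subject number, and visit in chronological order". Protocol 10.4.4 likewise describes the vital-signs display in terms of visits.

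**The concern.** A rule for choosing one record per day suits accidental repeats. It does not suit readings that the protocol deliberately spaces across the hours after a dose. The wording suggests that it was written for laboratory data: its tie-breakers refer to retests and accession numbers. SAP 5.2.3 carries an almost identical sentence for laboratory values ("In the case of multiple values in a visit day, data will be selected for analysis as described in" Section 3.5.6), and there the schedules plan one set per day, so the rule does no harm.

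For vital signs the rule always keeps the last planned reading of a dosing day, the one furthest from the dose. Safety and tolerability are the primary objective of this first-in-human study. A transient change in blood pressure or pulse between 2 and 8 h would be absent from every vital-signs summary by treatment and cohort. Cohorts have 6 active and 2 placebo subjects, and a dose-related pattern across cohorts is much harder to see in separate listings than in tables by hour.

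**Working it through.** The documents give no figure of their own to reproduce here. The check applies the written rule to the planned times and counts what is kept.

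**Inputs.** Times come from Appendices 1a, 1b and 2, footnote a. The analysis visit is the nominal study day (SAP 3.5.5; on treatment and follow-up days each schedule column is a single day). The latest post-Baseline record per visit day is kept (SAP 3.5.6). The Day 1 predose reading is taken as Baseline.

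**Part A, per subject and dosing period**

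- Day 1 holds 2, 4, 8 and 12 h. Days 2 to 7 hold one reading each (24 to 144 h).
- Planned post-dose sets: 4 + 6 = 10. Kept: 1 + 6 = 7. Left out: 2, 4 and 8 h = 3.
- Share left out: 3/4 = 75% on Day 1; 3/10 = 30% overall.
- Cohort A7 over two periods: 2 × 3 = 6 of 2 × 10 = 20, again 30%.

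**Part B, per subject, once-daily dosing assumed**

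- Post-dose sets on dosing days: 8 × 4 = 32. Kept: 8. Left out: 24 (75%).
- Adding 6 follow-up sets (1 to 5 days after the last dosing day, and end of study): 32 + 6 = 38. Left out: 24/38 = 63%.
- The predose readings on Days 2 to 8 are also post-Baseline and also lose to the 12 h reading. With these 7: 31 of 39 on dosing days (79%) and 31 of 45 overall (69%). Kept: 14 of 45.

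**Twice-daily dosing.** Appendix 2 footnote a gives no separate vital-signs schedule for this case.

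- If the hours run from the morning dose only, the count stays at 24 of 32 (75%).
- If the four hours were repeated after each dose, with two doses on Days 1 to 7 and one on Day 8, the planned sets would be 7 × 8 + 4 = 60. With 8 kept, 52 of 60 (87%) are left out. This is an assumed upper case.

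**Whole study, at full planned enrolment and once-daily dosing.** Readings at 2, 4 and 8 h left out of the tables:

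- Part A: 40 × 3 (A1 to A5) + 8 × 3 (A6) + 6 × 2 × 3 (A7) = 180.
- Part B: 16 × 24 = 384.
- Total: 564.

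**After the fix**, Part A would tabulate 10 of 10 post-dose sets instead of 7, and Part B 45 of 45 post-Baseline sets instead of 14.

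**The case against.** The strongest reply is that the text does not force this reading.

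- **The condition in 3.5.6.** The rule applies only if a single value is needed, and a table by nominal hour needs no single value per day. This does not remove the problem. SAP 5.3 specifies summaries by visit, and one mean or change per subject per visit does need a single value.
- **The trigger in 5.3.** It speaks of an analysis window, while 3.5.5 says that windowing is not used. This looks like carried-over wording. It shows that the cross-reference needs repair; it does not supply a time-point table.
- **The time-point wording in 3.5.4.** "Change from Baseline will be defined as the result at desired timepoint minus the result at Baseline" allows intraday time points. It is a general definition, however, and creates no row in the 5.3 tables.
- **Protocol 10.4.4.** It could be read as displaying everything recorded at a visit. It does not say so, and it names no time points.
- **Unseen material.** Table shells, and the appendices that the SAP contents list as Section 9, were not available for this check. They may show time points.

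What stands is that time-point tables may well be intended, so this is an unsuitable written rule and not proof of what the tables will contain. The limit on consequences also stands. No inference is planned, every reading remains in the listing, and abnormal vital signs with signs or symptoms are recorded as AEs if they meet the definition (protocol 9.7). The DRC's safety review is not governed by this rule, and vital signs are not named in the primary endpoint.

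**Conclusion.** The point holds. Applied as SAP 5.3 directs, the latest-record rule reduces each dosing day to its 12 h reading. It leaves 75% of same-day post-dose vital-sign sets out of the tables in both parts, or 30% of all post-dose sets in Part A. In Part B it leaves out 69% of all post-Baseline sets once predose readings are counted. The Part B figures assume once-daily dosing, and all figures assume that readings are taken as scheduled. Confidence is medium, because shells not seen here could override the text. The matter should be fixed, but its reach is limited to descriptive vital-signs summaries.

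**What to change.** In SAP 5.3, state that vital signs and change from Baseline are summarised by nominal day and hour. Restrict the latest-record rule in 3.5.6 to repeat measurements at the same nominal time point, and replace the reference to an analysis window, since none is used.

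A minor clarification belongs with this. The ECG shift table in SAP 5.5 is also by visit, although several ECGs are planned on some days, and it neither states a selection rule nor cites 3.5.6. It should say that it follows the same nominal time-point approach.

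The cost is a few sentences of SAP text and longer tables. No additional data are needed.

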4 SUBJECT DISPOSITION

4.1 Subject Enrollment and Disposition

A summary of subject enrollment will be provided by treatment and cohort. The summary will present the number and percentage of subjects enrolled. For each column, the denominator for the percentage calculation will be the total number of subjects analyzed for that column.

The randomization schedule used for the study will be provided as an appendix to the CSR.

A summary of subject disposition will be provided by treatment and cohort. This summary will present the number of subjects in each of the categories listed below:

- Randomized Set
- Full Analysis Set
- Safety Analysis Set

The number and percentage of the subjects in the following categories will be summarized using the Safety Analysis Set:

- Completed study drug
- Did not complete study drug and reasons for study drug discontinuation
- Completed study
- Did not complete the study and reasons for study discontinuation

For the status of study drug and study completion and reasons for discontinuation, the number and percentage of subjects in each category will be provided. The denominator for the percentage calculation will be the total number of subjects in the Safety Analysis Set corresponding to that column.

The following by-subject listings will be provided by cohort and subject number in ascending order:

- Reasons for premature study drug or study discontinuation.

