10.3 Analysis Populations

The following populations will be considered for analysis of various endpoints:

- **Randomized Set:** It includes all randomized subjects, classified according to the treatment to which they were randomized, regardless of the actual treatment received.
- **Full Analysis Set:** It includes all randomized subjects, classified according to the treatment to which they were randomized, regardless of the actual treatment received, who took at least 1 dose of study drug.
- **Safety Analysis Set:** It includes all subjects, classified according to the actual treatment received regardless of random assignment, who took at least one dose of study drug. This is the main analysis population for all safety analyses.
- **Pharmacokinetic-Evaluable Set:** It consists of all subjects, classified according to the actual treatment received regardless of random assignment, who receive at least 1 dose of study drug. At least 1 evaluable pharmacokinetic blood sample following a dose of study treatment is required for inclusion in this analysis. This is the main analysis population for all pharmacokinetic analyses.

Based on the actual deviations, the criteria for exclusion of subjects from the different data sets will be specified and updated, if necessary, prior to database lock.

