10.4.1 Disposition of the Study Subjects

The disposition of subjects will be described with summaries by treatment of the number of subjects in each analysis set described above, the number of subjects who completed the study, and the number of subjects for whom study drug was permanently discontinued (including the reasons for discontinuation). Randomized Analysis Set will be used to produce this analysis.

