3.1 Analysis Populations

Analysis populations or sets define the subjects to be included in an analysis. Analysis sets and their definitions are provided in this section. The analysis set will be identified and included as a subtitle of each table, figure, and listing. For each analysis set, the number and percentage of subjects eligible for inclusion will be summarized by treatment and cohort. A listing of reasons for exclusion from analysis sets will be provided by cohort and subject.

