3.1.3 Safety Analysis Set

The Safety Analysis Set includes all randomized subjects, classified according to the actual treatment received regardless of randomized assignment, who took at least 1 dose of study drug. This is the main analysis set for all safety analyses.

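### SAP 4.1 puts completion and discontinuation on the Safety Analysis Set where protocol 10.4.1 specifies the Randomized Set, so a randomized, never-dosed subject is missing from those rows and denominators

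*Combined protocol and SAP*

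**What the plan says.** Protocol 10.4.1 defines disposition as the number of subjects in each analysis set, together with "the number of subjects who completed the study, and the number of subjects for whom study drug was permanently discontinued", including the reasons for discontinuation. It names the population: "Randomized Analysis Set will be used to produce this analysis". Protocol 10.3 calls this the Randomized Set and defines it: "It includes all randomized subjects, classified according to the treatment to which they were randomized, regardless of the actual treatment received".

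SAP 4.1 splits the table in two.

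- The first block gives set sizes for the Randomized Set, Full Analysis Set and Safety Analysis Set: "This summary will present the number of subjects in each of the categories listed below".
- The second block holds study-drug completion, study completion, non-completion and reasons. For it, "The number and percentage of the subjects in the following categories will be summarized using the Safety Analysis Set", and "The denominator for the percentage calculation will be the total number of subjects in the Safety Analysis Set corresponding to that column".

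SAP 3.1.3 defines the Safety Analysis Set as randomized subjects "classified according to the actual treatment received regardless of randomized assignment, who took at least 1 dose of study drug". SAP 3.2 adds that actual treatment is taken to differ from randomized treatment only if it differed throughout the subject's treatment.

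I find no acknowledgement of, or reason for, the change of set in the SAP text available to me.

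**The concern.** The two documents give different populations for the same analysis, and the difference matters for the purpose of a disposition table, which is to account for everyone randomized. The Safety Analysis Set drops subjects who were never dosed, and it regroups subjects by what they received. Completion rates computed on it are conditional on having been dosed. A loss between randomization and dosing cannot appear as a non-completion and carries no reason in the table.

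Arms here have 6 active and 2 placebo subjects, so a single subject moves a percentage a long way. The SAP is also uneven across adjacent sections: SAP 4.2 reports eligibility failures and important protocol deviations on the Randomized Set. The same treatment-by-cohort column could therefore carry one N in the deviation table and another in the completion rows.

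**Working it through.** Neither document states a completion rate or an expected number of undosed subjects, so there is no figure to reproduce. The check compares the two definitions and then illustrates the size of the difference.

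**Step 1: the definitions side by side**

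| | Protocol 10.4.1 with 10.3 | SAP 4.1 with 3.1.3 and 3.2 |
|---|---|---|
| Population for completion and discontinuation | Randomized Set | Safety Analysis Set |
| Dose required | No | At least 1 |
| Grouping | As randomized | As treated |
| Study-drug discontinuation covered | Yes | Yes |

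The sets differ in two ways only: undosed subjects, and subjects whose whole treatment was the wrong one.

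**Step 2: can a subject be randomized and not dosed?** Protocol 8.2.2 randomizes on Day 1 after the predose assessments, so the window is short. It is not empty. Protocol 7.2 halts drug administration in a cohort when a safety trigger is met, and a subject already randomized that day could then go undosed. A subject could also withdraw in the window. The documents give no rate for either.

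**Step 3: size for one undosed subject.** Inputs are the 6:2 allocation in cohorts of 8 (protocol 4.1.1 and 4.1.2). Assumptions are one undosed subject (u = 1) in the group shown, and all others completing. With n randomized, completion is (n − u)/n on the Randomized Set and (n − u)/(n − u) on the Safety Analysis Set.

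- Active arm, n = 6: 5/6 = 83.3% against 5/5 = 100%. Non-completion is 1/6 = 16.7% against 0/5 = 0%.
- Placebo arm, n = 2: 1/2 = 50.0% against 1/1 = 100%. Non-completion is 1/2 = 50.0% against 0/1 = 0%.
- Both arms pooled, n = 8: 7/8 = 87.5% against 7/7 = 100%. The SAP table is by treatment and cohort, so the arm figures are the relevant ones.

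Protocol 7.1.2 lets subjects withdrawn for reasons other than a drug-related AE be replaced. If an undosed active subject were replaced within the same arm, that arm would show 6/6 = 100% instead of 6/7 = 85.7%.

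**Step 4: regrouping.** In Cohorts A1–A5 treatment is one dose, so a single wrong dose is a difference throughout treatment under SAP 3.2. If one placebo subject received active drug, the columns would be 6 and 2 on the Randomized Set but 6 + 1 = 7 and 2 − 1 = 1 on the Safety Analysis Set. In Part B the subject would have to receive the wrong treatment throughout the 8-day course, which is much less likely.

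**Step 5: the null case.** With u = 0 and no mis-dosing, both sets contain the same subjects in the same arms, and every figure agrees.

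**The case against.** The strongest reply is that nothing is hidden. The set-size block of the same table shows the Randomized Set count, so an active arm with one undosed subject reads 6 randomized against 5 in the Safety Analysis Set. SAP 3.1 adds: "A listing of reasons for exclusion from analysis sets will be provided by cohort and subject". SAP 4.1 also promises a by-subject listing of reasons for premature discontinuation, with no stated restriction to dosed subjects. This stands. A reader might infer that the undosed subject vanishes from the disposition table altogether, and the documents do not support that. What remains is narrower: a gap between two counts plus a listing is not the completion and discontinuation summary on randomized subjects that the protocol specifies.

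Three further inferences also go too far.

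- **Failed Day 1 checks.** It is tempting to say that subjects stopped by Day 1 predose results are lost. Protocol 8.2.2 places randomization after those assessments, so such subjects are in neither set.
- **Missing PK count.** Protocol 10.4.1 asks for the count in every analysis set defined in 10.3, and SAP 4.1 omits the PK-Evaluable Set. But SAP 3.1.4 defers PK sets to a separate PK analysis plan, so this is a deferral that needs a cross-reference, not a demonstrated omission.
- **Effect on the primary safety result.** Protocol 10.3 and SAP 5.1.6 both put safety analyses on the Safety Analysis Set, and that choice is not in question. The study is descriptive, and dose decisions rest on the Data Review Committee's review of safety and PK data, not on this table.

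Finally, the event is uncommon by design, since dosing follows randomization on the same day. That limits the likelihood, not the inconsistency.

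**Conclusion.** The concern holds as a contradiction between protocol 10.4.1 and SAP 4.1 on the population, denominator and grouping for completion and discontinuation. As the SAP is written, a randomized, never-dosed subject is counted among those randomized but is absent from the completion and discontinuation rows, their reasons and their denominators. A mis-dosed subject in a single-dose cohort is counted in the other arm.

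The size depends on events whose frequency the documents do not give. One undosed subject raises reported completion by 100 − 83.3 = 16.7 percentage points in an active arm of 6 and by 100 − 50 = 50 points in a placebo arm of 2, if everyone else completes. With no such event the effect is zero. It is a reporting point worth correcting before database lock, and it does not bear on the validity of the safety or PK conclusions.

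**What to change.** In SAP 4.1:

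1. Use the Randomized Set, by randomized treatment, as population and denominator for all completion and discontinuation rows and their reasons. Include the study-drug rows: protocol 10.4.1 covers drug discontinuation in the same analysis, so leaving them on the Safety Analysis Set would keep part of the contradiction.
2. Add a row for subjects randomized but not dosed, with the reason. Neither document requires it, but without it an undosed subject fits poorly under either completing or discontinuing drug.
3. Give the PK-Evaluable Set count, or cross-refer to the PK analysis plan.

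Use one name for the set: protocol 10.4.1 says Randomized Analysis Set, while protocol 10.3 and the SAP say Randomized Set. If the sponsor prefers the Safety Analysis Set for these rows, the SAP should state the departure from the protocol and justify it.

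The cost is SAP wording and one table shell. No new data are needed.
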